#### Pregnancy Test (as detailed in Section 9.2.7)

- Collection of acute kidney injury, ascites and variceal haemorrhage data
- AE assessment (as detailed in Section 11)
- Concomitant medication assessment (as detailed in Section 9.2.10)
- Biomarker (as detailed in Section 9.2.8.3)

For discharged patients, the IMP or placebo will be returned and further IMP or placebo will be supplied to the patient. The patient should take their next dose of IMP or placebo as soon as all visit assessments have been completed. The capsule will continue to be administered twice-daily.

In addition, the following assessments of nutritional status will also be performed, with nutritional interventions provided where required:

- BMI
- Bedside Subjective Global Assessment (SGA) score (0, 1, 2, and 3). Patients will be classified into the following categories:
  - Well nourished (0)
  - Mild malnutrition (1)
  - Moderate malnutrition (2)
  - Severe malnutrition (3)

#### 8.2.8 Visit 7/Day 21

The following assessments will be performed:

- Physical examination (as detailed in Section 9.2.2)
- Vital signs (blood pressure, heart rate and body temperature), as detailed in Section 9.2.4);
- Pharmacokinetic sampling (as detailed in Section 9.2.8.1)
- Samples for clinical laboratory safety tests (haematology, serum biochemistry, and coagulation tests as detailed in Section 9.2.5)
- MELD ( as detailed in Section 9.1.1)
- MDF (as detailed in Section 9.1.7)

- m-SOFA (as detailed in Section 9.1.8)
- APACHE II score (as detailed in Section 9.1.9)
- Total bilirubin (as detailed in Section 9.1.2)
- CK-18 (as detailed in Section 9.1.6)
- AST:ALT (as detailed in Section 9.1.3)
- Child pugh score (as detailed in Section 9.1.5)
- Gamma GT (as detailed in Section 9.1.4)
- 
- Collection of acute kidney injury, ascites and variceal haemorrhage data
- AE assessment (as detailed in Section 11)
- Concomitant medication assessment (as detailed in Section 9.2.10)
- Biomarker (as detailed in Section 9.2.8.3)
- Lille score assessment (as detailed in Section 9.1.10)
- West Haven criteria assessment (as detailed in Section 9.1.11)

For discharged patients, the IMP or placebo will be returned and further IMP or placebo will be supplied to the patient. The patient should take their next dose of IMP or placebo as soon as all visit assessments have been completed. The capsule will continue to be administered twice-daily.

### **8.2.9 Visit 8/Day 28/Early Termination**

The following assessments will be performed:

- Physical examination (as detailed in Section 9.2.2)
- Vital signs (blood pressure, heart rate and body temperature), as detailed in Section 9.2.4);
- ECG (as detailed in Section 9.2.3)
- Pharmacokinetic sampling (as detailed in Section 9.2.8.1)
- Exploratory blood sampling (as detailed in Section 9.2.8.2)
- Samples for clinical laboratory safety tests (haematology, serum biochemistry, and coagulation tests as detailed in Section 9.2.5)
- Pregnancy test (as detailed in Section 9.2.7)
- MELD (as detailed in Section 9.1.1)
- MDF (as detailed in Section 9.1.7)
- m-SOFA (as detailed in Section 9.1.8)
- APACHE II score (as detailed in Section 9.1.9)
- Total bilirubin (as detailed in Section 9.1.2)
- CK-18 (as detailed in Section 9.1.6)
- AST:ALT (as detailed in Section 9.1.3)
- Child pugh score (as detailed in Section 9.1.5)

- Gamma GT (as detailed in Section 9.1.4)
- Biomarker (as detailed in Section 9.2.8.3)
- West Haven criteria assessment (as detailed in Section 9.1.11)
- Lille score assessment (as detailed in Section 9.1.10)
- Collection of acute kidney injury, ascites and variceal haemorrhage data
- AE assessment (as detailed in Section 11)
- Concomitant medication assessment (as detailed in Section 9.2.10)

In addition, the following assessments of nutritional status will also be performed, with nutritional interventions provided where required:

- BMI
- Bedside Subjective Global Assessment (SGA) score (0, 1, 2, and 3). Patients will be classified into the following categories:
  - Well nourished (0)
  - Mild malnutrition (1)
  - Moderate malnutrition (2)
  - Severe malnutrition (3)

The IMP or placebo will be returned. Further IMP or placebo will not be supplied to the patient.

On completion of this visit, patients will be advised that they will be required to return to the investigational site in 62 days at Visit 9 for final assessment.

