## 6 STUDY DESIGN

### 6.1 General

This is a randomised, placebo-controlled, double-blind, parallel group, multicentre, exploratory phase II study preceded by an open label pilot phase to investigate the efficacy and safety of orally administered DS102 capsules in patients with acute decompensated AH aged over 18 years.

After the completion of the open-label phase of the study the DSMB will evaluate the safety and pharmacokinetic data and might recommend a dose adjustment for the double blind randomised phase of the study

After the open-label pilot phase of the study during which six patients will be enrolled, two parallel groups of patients will be enrolled into the randomised double-blind phase of the study to compare one dose of DS102 with placebo over a 28 day treatment period. Patients will receive standard of care therapy in addition to their assigned IMP throughout the treatment period of the study. It is planned that 120 evaluable patients, 60 per treatment group, will be randomised.

Both parts of the study, the open label phase and the double blind phase of the study consist of a screening period of up to five days (at the discretion of the investigator), a 28 day treatment period and a follow up period until day 90 after start of treatment. Screening is to commence upon admission to hospital; at the screening visit, after giving informed consent to participate, patients will be assessed using the screening examinations.

A schematic diagram of the overall timeframe of the study is given in Figure 3.

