## 7.5 Withdrawal of Patients

Patients have the right to withdraw from the study at any time for any reason, without repercussion. The Investigator must explain this to the patient and that this will in no way prejudice their future treatment. The investigator also has the right to withdraw patients from the study if she/he feels it is in the best interest of the patient or if the patient is uncooperative or non-compliant. It is understood by all concerned that an excessive rate of withdrawal can render the study un-interpretable, therefore, unnecessary withdrawal of patients should be avoided. Should a patient decide to withdraw, all efforts will be made to complete and report the observations, particularly the follow-up examination, as thoroughly as possible.

In the event of patient withdrawal, the Investigator or one of his or her staff members should talk to the patient or in case of hospital discharge contact the patient either by telephone or through a personal visit to determine as completely as possible the reason for the withdrawal, and record the reason in patient's source document and case report form (CRF). A complete final early termination evaluation at the time of the patient's withdrawal should be made with an explanation of why the patient is withdrawing from the study. If the reason for removal of a patient is an adverse event (AE) or an abnormal laboratory test result, the principal specific event or test will be recorded.

Please note: the patient is allowed not to give a reason for withdrawal. If this is the case this must be recorded as well.

Patients who discontinue the study before Day 28 visit and are discharged from the hospital will be asked to come for an early termination visit as soon as possible and have the assessments listed at Day 28 performed. Mortality will be assessed throughout to Day 90.

There will be two main categories for withdrawals from the study: "complete withdrawal" and "withdrawals from investigational product".

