## 8 STUDY CONDUCT

### 8.1 Study Schedule

During the study, 8 visits to the clinic are scheduled after the screening visit (Visit 1): one at the start of the comparative treatment period (Baseline/Visit 2) and six in the comparative treatment period (Visit 3/Day 3, Visit 4/Day 5, Visit 5/Day 7, Visit 6/Day 14, Visit 7/Day 21, Visit 8/Day 28 or Early Termination).

A final safety follow-up visit (Visit 9/Day 90) will be conducted on Day 90.

For patients who discontinue the study early, for whatever reason, the Early Termination visit (Visit 8) will be performed. Patients who discontinue the study before Day 28 and are already discharged from the hospital will be asked to attend the investigative site as soon as possible that assessments scheduled for Visit 8 can be conducted. These patients will be asked also to attend a final safety follow-up visit (Visit 9/Day 90).

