6.13 Exploratory Endpoints

6.13.1 Survival at day 7, 14, 21, 28 and 90

Survival time will be derived as:

(Death date/last date patient known to be alive – date of randomisation + 1).

Survival time will be analysed with a Cox proportional hazards model including covariates for treatment group and baseline MELD score. Tied observations will be

handled using the Breslow-Henshaw method. The assumption of proportional hazards will be assessed visually using the log-log plot.

Estimates for the hazard ratio (DS102:Placebo), associated 95% CI and p-values will be presented.

Estimates of survival rate and associated 95% CI at days 7, 14, 21, 28 and 90 will be presented for each treatment group.

Kaplan-Meier plot of the probability of survival against time (days) will be presented for each treatment group.

6.13.2 Change in GT from baseline to day 7, 14, 21 and 28

Gamma glutamyl transferase is a liver enzyme indicative of liver dysfunction and alcohol intake.

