6.13.6.2 Descriptive summaries and listing

Lille score observed values, absolute change from baseline and percentage change from baseline will be listed and summarised by treatment group and visit.

6.13.7 Combination of change of MELD score from baseline, premature treatment terminations and mortality

A 5-level ordinal variable combining change of MELD score from baseline, premature treatment terminations and mortality will be derived.

Each patient will be allocated to the lowest/worst level that occurred.

Level 1: death within 28 days using survival time derived in section [6.13.1](#)

Level 2: death within 90 days using survival time derived in section [6.13.1](#)

Level 3: early termination because of safety issues or lack of efficacy

Level 4: no improvement in MELD score at day 28 compared to baseline (classed as less than 25% reduction in MELD score from baseline to day 28).

Level 5: improvement in MELD score at day 28 compared to baseline (classed as greater than or equal to a 25% reduction in MELD score baseline to day 28).

Patients who are lost to follow up within 28 days and therefore do not have a day 28 MELD score will be allocated to level 4 or 5 depending on their imputed result at day 28 based on the model in section [6.11.1](#) under a missing at random (MAR) assumption.

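### The 62-day return instruction at the combined Day 28/Early Termination visit reaches Day 90 only from Day 28, and contradicts the Day 90 anchor for early terminators

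*Protocol*

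**What the plan says.** The section in question is headed "8.2.9 Visit 8/Day 28/Early Termination", so one text serves two kinds of patient: those who reach Day 28 and those who stop earlier. It closes by saying that "patients will be advised that they will be required to return to the investigational site in 62 days at Visit 9 for final assessment". No separate interval is given for an ET visit.

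Elsewhere Visit 9 is tied to the calendar of the trial, not to Visit 8:

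- Protocol 6.1 describes "a follow up period until day 90 after start of treatment".
- Protocol 8.1 states: "A final safety follow-up visit (Visit 9/Day 90) will be conducted on Day 90". On patients who stop before Day 28 it adds: "These patients will be asked also to attend a final safety follow-up visit (Visit 9/Day 90)".
- Both flow charts (Appendices 1 and 2) put Visit 9 at Day 90 with a window of ±10 days.

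Protocol 8.2.2 has the Visit 8 procedures done soon after withdrawal, so an ET visit can fall on any day before Day 28. For patients who discontinue, Protocol 7.5 says: "Mortality will be assessed throughout to Day 90".

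In the SAP, survival time (6.13.1) runs from randomisation to "Death date/last date patient known to be alive". The ordinal variable (6.13.7) uses the same quantity: "Level 2: death within 90 days using survival time derived in section" 6.13.1.

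**The concern.** The figure of 62 days looks like Day 90 minus Day 28, written for completers and left in place for early terminators. For anyone whose ET visit is before Day 28, a fixed 62-day interval and a Day 90 visit cannot both be met.

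What is at stake is the length of follow-up in one subgroup. If Visit 9 takes place early and nothing else is learned about the patient afterwards, the last known-alive date stops short of Day 90. In the Cox and Kaplan-Meier analyses the patient is censored at that date. The ordinal variable has no censoring: a patient who died after the early visit but by Day 90, with the death unknown to the site, would be placed in level 3, 4 or 5 instead of level 2. Laboratory and score values from that visit would also be filed as Day 90 values although taken earlier.

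**Working it through.** **Inputs**

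- Return interval: 62 days from completion of Visit 8 (Protocol 8.2.9).
- Target: Day 90 from the start of treatment, Day 0 (Protocol 6.1, 8.1).
- Visit 9 window: ±10 days (Appendices 1 and 2), so 90 − 10 = Day 80 to 90 + 10 = Day 100.
- Visit 8 window at Day 28: ±1 day (same appendices).
- Day of the ET visit: d, which can be below 28 (Protocol 8.2.2).

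**Reproducing the plan's figure.** 90 − 28 = 62, so the interval is exact for a Day 28 visit. At the edges of the Visit 8 window, 27 + 62 = 89 and 29 + 62 = 91, both well inside Day 80–100.

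**ET visit on Day d**

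- Return day under 8.2.9 = d + 62.
- Shortfall from Day 90 = 90 − (d + 62) = 28 − d.
- Return is before the window when d + 62 < 80, that is d < 18.
- Interval that would reach Day 90 = 90 − d.

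| ET visit, Day d | Return day, d + 62 | Days short of 90 | In Day 80–100? | Interval needed, 90 − d |
|---|---|---|---|---|
| 3 | 65 | 25 | No | 87 |
| 5 | 67 | 23 | No | 85 |
| 7 | 69 | 21 | No | 83 |
| 14 | 76 | 14 | No | 76 |
| 17 | 79 | 11 | No | 73 |
| 18 | 80 | 10 | Yes, first day | 72 |
| 21 | 83 | 7 | Yes | 69 |
| 28 | 90 | 0 | Yes | 62 |

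The clock runs from the ET visit, not from the decision to stop. Patients already discharged are asked back as soon as possible, so d may be some days later than the termination itself.

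**Carrying it into the analysis.** Take an ET visit on Day 7 and a return on Day 69. With randomisation on Day 0 and no later information, the SAP formula gives a censored survival time of 69 − 0 + 1 = 70 days. If that patient dies on Day 80 and the site does not learn of it, the survival analyses hold a censored record, and the ordinal variable holds a level from 3 to 5 where level 2 is correct.

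**The case against.** The strongest reply is that this is one loose sentence against several consistent ones. Protocol 6.1, the heading of 8.2.10 and both flow charts all say Day 90, and 8.1 says it for exactly the patients concerned. Even 8.2.9 names Visit 9, which is defined as Day 90. A site that schedules from 8.1 or the flow chart gets it right. This stands: a reader might infer from 8.2.9 alone that early terminators will be recalled early, and the documents do not support that. They support only a contradiction that could lead sites to schedule differently. It does not dispose of the point, because 8.2.9 is the sentence that tells staff what to say to the patient at the ET visit.

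A second reply is that mortality does not depend on the date of Visit 9. Protocol 7.5 requires it through Day 90 for patients who discontinue, the flow charts have their own mortality row, Protocol 11.1.4 extends event reporting through follow-up, and the SAP uses the date of death or of last known survival, not the visit date. This largely stands. It would go too far to say that deaths will be missed, or that Visit 9 ends all contact with the patient. Against it, the protocol describes no contact between the ET visit and Day 90 other than the scheduled visits at which the flow charts mark mortality, so the requirement in 7.5 has no stated mechanism of its own.

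Third, the group is narrow. Complete withdrawals (Protocol 7.5.1) stop all evaluations. Patients withdrawn only from study product (7.5.2) continue their visits and need not have an early ET visit. ET visits from Day 18 on stay within a window the protocol already accepts for everyone. All of this stands.

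**Conclusion.** The contradiction is real, and the arithmetic is exact. The 62-day instruction agrees with Day 90 only from Day 28, falls short by 28 − d days after an ET visit on Day d, and falls before the protocol's own window when d is below 18.

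Its reach is limited. The primary endpoint and the score and laboratory models run to Day 28 and are untouched. What could be affected is Day 90 survival, which is exploratory, and level 2 of the ordinal variable, which Protocol 12.8.3 calls secondary and the SAP places among the exploratory endpoints. An error there needs four things together: a site that follows 8.2.9 literally, a patient who survives to Day d + 62, a death after that visit but by Day 90, and no other route by which the site learns of it.

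The number of patients affected cannot be derived from the documents. A reader might assume that 5–15% have an ET visit before Day 18 and arrive at 0.05 × 120 = 6 to 0.15 × 120 = 18 patients. That rate is an assumption only, and the result still includes complete withdrawals, patients who die before Day d + 62 and patients at sites that follow 8.1. Nor do the documents show that early terminators die more often or that termination rates differ by arm, so a bias between arms is possible but not established.

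The correction is worth making because it is nearly free.

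**What to change.** Reconcile 8.2.9 with 6.1 and 8.1 by using the protocol's own day and window. In 8.2.9, replace the 62-day interval with: *on Day 90 (±10 days) counted from the start of treatment (Day 0), whatever the date of the Day 28 or Early Termination visit*. Have the eCRF compute the Visit 9 date from Day 0, so that sites do not count forward from Visit 8.

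The cost is one protocol sentence and one date calculation in the eCRF. No visit is added, and the SAP needs no change.

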### **8.2.10 Visit 9/Day 90/Follow Up**

In case of the patient's survival the following assessments will be performed:

- Physical examination (as detailed in Section 9.2.2)
- Vital signs (blood pressure, heart rate and body temperature), as detailed in Section 9.2.4);
- Samples for clinical laboratory safety tests (haematology, serum biochemistry, and coagulation tests as detailed in Section 9.2.5)
- MELD ( as detailed in Section 9.1.1)
- MDF (as detailed in Section 9.1.7)
- m-SOFA (as detailed in Section 9.1.8)
- West Haven criteria assessment (as detailed in Section 9.1.11)
- Lille score assessment (as detailed in Section 9.1.10)
- APACHE II score (as detailed in Section 9.1.9)
- Total bilirubin (as detailed in Section 9.1.2)
- CK-18 (as detailed in Section 9.1.6)

---

- AST:ALT (as detailed in Section 9.1.3)
- Child pugh score (as detailed in Section 9.1.5)
- Gamma GT (as detailed in Section 9.1.4)

## 9 ASSESSMENTS

### 9.1 Efficacy Assessments

#### 9.1.1 Model for End-Stage Liver Disease

The model for end-stage liver disease (MELD) is employed in the evaluation of hepatic function and the assessment of prognosis. MELD is calculated based on variables including the international normalised ratio (INR), serum creatinine, and serum bilirubin.

A MELD score  $\geq 18$  (within 24 hours of presentation) is considered a good predictor of 90 day mortality in patients with AH.

MELD will be assessed at Visit 1/Screening, Visit 2/Baseline, Visit 3/Day 3, Visit 4/Day 5, Visit 5/Day 7, Visit 6/Day 14, Visit 7/Day 21, Visit 8/Day 28/Early Termination and Visit 9/Day 90/Follow up.

#### 9.1.2 Total Bilirubin

Total bilirubin concentration is a marker of hepatic function.

Blood samples will be taken to assess total bilirubin at Visit 1/Screening, Visit 2/Baseline, Visit 3/Day 3, Visit 4/Day 5, Visit 5/Day 7, Visit 6/Day 14, Visit 7/Day 21, Visit 8/Day 28/Early Termination and Visit 9/Day 90/Follow up.

#### 9.1.3 ALT, AST, AST:ALT Ratio

Increased liver enzymes (alanine aminotransferase (ALT) and aspartate aminotransferase (AST)) are a marker of liver injury and will be assessed at all time points.

Blood sample will be taken to assess ALT, AST, and AST:ALT ratio at Visit 1/Screening, Visit 2/Baseline, Visit 3/Day 3, Visit 4/Day 5, Visit 5/Day 7, Visit 6/Day 14, Visit 7/Day 21, Visit 8/Day 28/Early Termination and Visit 9/Day 90/Follow up.

#### 9.1.4 Gamma Glutamyl Transferase

Gamma glutamyl transferase (GGT) is a liver enzyme indicative of liver dysfunction and alcohol intake.

Gamma GT levels will be assessed as part of serum biochemistry at Visit 2/Baseline, Visit 3/Day 3, Visit 4/ Day 5, Visit 5/Day 7, Visit 6/Day 14, Visit 7/Day 21, Visit 8/Day 28/Early Termination and Visit 9/Day 90/Follow up.

#### 9.1.5 Child-Pugh Score

The Child-Pugh score is a means of assessing the severity of chronic liver disease, including cirrhosis, based on five clinical parameters, each of which is allocated a score; total score indicates the severity and prognosis of chronic liver disease.

**Table 1: Child-Pugh Score (Jackson & Gleeson 2010)**

Factor	1 point	2 points	3 points
Bilirubin ( $\mu\text{mol litre}^{-1}$ )	< 34	34–50	< 50
Albumin (g litre $^{-1}$ )	> 35	28 – 35	< 28
INR	< 1.7	1.7 – 2.2	> 2.2
Ascites	None	Controlled	Refractory
Hepatic encephalopathy	None	I – II or controlled	III – IV or refractory

Blood samples will be taken to assess the Child-Pugh score at Visit 2/Baseline, Visit 3/Day 3, Visit 4/Day 5, Visit 5/Day 7, Visit 6/Day 14, Visit 7/Day 21, Visit 8/Day 28/Early Termination and Visit 9/Day 90/Follow up.

#### **9.1.6 Cytokeratin-18 M30/M65**

Cytokeratin(CK)-18 M30 and M65 are biomarkers of hepatocyte apoptosis and total cell death, respectively, and are employed in the detection of fibrosis and steatosis.

Blood samples will be taken to perform this assessment at Visit 2/Baseline, Visit 3/Day 3, Visit 4/Day 5, Visit 5/Day 7, Visit 6/Day 14, Visit 7/Day 21, Visit 8/Day 28/Early Termination and Visit 9/Day 90/Follow up.

#### **9.1.7 Maddrey Discriminant Function**

The Maddrey discriminant function (MDF) is a measure of liver dysfunction and a method of assessing disease severity.

MDF is calculated as follows:

$$\text{MDF} = 4.6 \text{ (patient's PT} - \text{control PT}) + \text{total bilirubin (mg/dl)}$$

MDF will be assessed at Visit 1/Screening, Visit 2/Baseline, Visit 3/Day 3, Visit 4/Day 5, Visit 5/Day 7, Visit 6/Day 14, Visit 7/Day 21, Visit 8/Day 28/Early Termination and Visit 9/Day 90/Follow up.

#### **9.1.8 Modified Sequential Organ Failure Assessment**

The m-SOFA score is used in the assessment of disease severity, as well as in predicting outcome and is classified as follows:

Organ System	0	1	2	3	4
Respiratory SpO 2 /FiO 2	>400	≤400	≤315	≤235	≤150
Liver	No scleral icterus or jaundice			Scleral icterus or jaundice	
Cardiovascular, hypotension	No hypo- tension	MAP <70 mm Hg	dopamine≤5 or dobutamine any dose	dopamine>5 epinephrine≤0.1 norepinephrine≤0.1	dopamine>15 epinephrine>0.1 norepinephrine>0. 1
CNS, Glasgow Coma Score	15	13-14	10-12	6-9	<6
Renal, Creatinine mg/dL	<1.2	1.2-1.9	2.0-3.4	3.5-4.9	>5.0

m-SOFA will be assessed at Visit 2/Baseline, Visit 3/Day 3, Visit 4/Day 5, Visit 5/Day 7, Visit 6/Day 14, Visit 7/Day 21, Visit 8/Day 28/Early Termination and Visit 9/Day 90/Follow up.

